Investigational Device and procedure	
MINIject is an integrated system comprising a minimally-invasive Glaucoma Drainage Implant and a Delivery Tool.
 
The Delivery Tool is configured for inserting the implant into the sub-scleral location through an ab-interno minimally-invasive approach. It is single-use.
 
Device options to be evaluated in this study:
 
Implant CS 600 with Curved Shaft.
 
Intervention:
 
The intervention is to be performed stand-alone.

Indication	
MINIject is indicated in adult, male and female patients diagnosed with open angle glaucoma, and where the progression of glaucoma is not adequately controlled by topical hypotensive medications.
 
MINIject is intended to be used to reduce the intraocular pressure (IOP) by channeling aqueous humor out of the anterior chamber to a sub-scleral location, thus enhancing the physiological uveoscleral outflow.

Synopsis

Design

Baseline and evaluation time points:

Screening / Baseline	Follow-up 1 day / 1 week / 2 weeks / 1 Month / 3 Months	Follow-up 6 / 12 / 18 / 24 Months
patient inclusion	Safety evaluation	safety and efficacy evaluation
medicated diurnal IOP baseline	single point IOP measurement	medicated diurnal IOP

This prospective, non-comparative, open, multi-center, interventional clinical investigation is designed as one cohort study and intended to show the efficacy and safety of the MINIject system consisting of the CS 600 MINIject implant and the delivery tool with curved shaft.

In total 25 patients will be enrolled in approximately 5 sites in Panama, India and Europe (France or Germany).

The study will evaluate the efficacy and safety of the implant and IOP lowering effects with or without glaucoma medications. The procedure will be a stand-alone surgery. Overall, the patient will be asked to attend at 10 visits and perform several examinations up to 24 months after surgery.

The primary efficacy objective of the present study is to show the IOP reduction under medication 6 months after surgery compared to medicated diurnal IOP at screening.

The sponsor will evaluate the ease of use of the delivery tool based on questionnaires completed by the surgeons after surgery.

Primary study objective

The primary objective is to show a reduction in medicated diurnal IOP between screening/baseline visit and medicated diurnal IOP at 6 months after surgery.

Secondary study objectives

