Clinically significant intra-ocular inflammation or infection, presence of ocular disease such as uveitis, ocular infection, severe dry eye, severe blepharitis, active proliferative/inflammatory retinopathy in the study eye.

Presence of silicone oil in the study eye.

Patients treated with systemic acetazolamide within 3 days before screening visit.

Patients with poor vision (LogMar score: +1.0) in non-study eye, unless there is an expected benefit for the study eye, in the opinion of the investigator.

Participation in any study involving an investigational drug or device within the past 3 Months.

Only for women of childbearing potential: positive urine pregnancy test at screening.

Individuals under tutorship or trusteeship.

Quality Assurance	During the clinical investigation, the sites will be visited by CRO staff to review the progress of the clinical investigation, review the data collected, conduct source data verification, (according to ISO 14155:2011(E); define the extend of source data verification) perform device accountability, identify issues and address their resolution. The aim of the monitoring of the clinical investigation is to ensure that the data collected is authentic, accurate and complete, to ensure the safety of the subjects and that the subject's rights are protected, and to ensure that the clinical investigation is performed according to the approved clinical investigation plan and all applicable regulations and guidelines.
--------------------------	---

Sample Size	Sample size is obtained by a paired sample t-test, 2-sided, with alpha of 0.05 and power of 0.9. The difference of interest is taken equal to 5.2 mmHg. Under the conservative assumption that 25% of subjects will drop out of the study, this treatment effect will be reduced to $0.75*5.2 = 3.9$ mmHg if all patients are included in an ITT analysis. The variance of the difference in IOP between the month 6 visit and baseline is assumed to be at most equal to $3^2+5^2=34$, hence the standard deviation is taken equal to 5.83. Under these assumptions, the sample size required is equal to 25 patients.
--------------------	--

Statistical rationale for sample	An IOP reduction $\geq 20\%$ has been previously used as success criterion and thus can be defined as clinically meaningful.
---	--

Synopsis

size calculation

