The mean baseline IOP of $26.0 \text{ mmHg} \pm 3.0$ used for calculation is derived from published study results involving comparable study population; subjects with OAG uncontrolled by medication(s).

The mean IOP at 6 months is estimated to $20.8 \text{ mmHg} \pm 5$, the standard deviation is derived from published study results involving comparable devices.

Based on these assumptions, the estimated sample size of 25, in order to obtain 16 completed subjects at 6 Months follow-up (endpoint for the primary objective).

Synopsis

FLOW CHART

	Visit 0	Visit 1	Visit 2	Visit 3	Visit 4	Visit 5	Visit 6	Visit 7	Visit 8	Visit 9	Visit 10
	Screen/ Baseline	Surgery	1 Day	1 week	2 weeks	1 Month Safety evaluation	3 Months	6 Months Safety & Efficacy evaluation	12 Months Safety & Efficacy evaluation	18 Months Safety & Efficacy evaluation	24 Months Safety & Efficacy evaluation
GENERAL ASSESSMENTS	Day - 42 to -1	Day 0	Day 1	Day 5-9	Day 12-16	Day 21-35	Day 70-98	Day 168-196	Day 335-425	Day 510-600	Day 700-790
Signed informed consent	X										
Demography/ relevant medical and ocular history/Glaucoma diagnosis	X										
Inclusion /exclusion criteria	X										
Urine pregnancy test (women of childbearing potential only)	X										
Concomitant ocular & non-ocular medications,	X	X	X	X	X	X	X	X	X	X	X
AE/SAE recording	X	X	X	X	X	X	X	X	X	x	X
Implantation		X									
Implant position assess by investigator's judgment		X									
Record video of surgery		X									
Ease of use feedback questionnaires completed by investigator		X									
QOL questionnaire, CIGTS sub-part	X							X	X	X	X

Synopsis

	Visit 0	Visit 1	Visit 2	Visit 3	Visit 4	Visit 5	Visit 6	Visit 7	Visit 8	Visit 9	Visit 10
OCULAR ASSESSMENTS	Screening/ Baseline	Surgery	1 day	1 week	2 weeks	1 Month Safety evaluation	3 Months	6 Months Safety & Efficacy evaluation	12 Months Safety & Efficacy evaluation	18 Months Safety & Efficacy evaluation	24 Months Safety & Efficacy evaluation
	Day -42 to -1	Day 0	Day 1	Day 5-9	Day 12-16	Day 21-35	Day 70-98	Day 168-196	Day 335-425	Day 510-600	Day 700-790
	BCVA	X		X	X	X	X	X	X	x	X
IOP, Goldmann Appl. Tonometry, diurnal (8:00 AM, 12:00 AM, 4:00 PM)	X							X	X	x	X
IOP (Single time point)			X	X	X	X	X				
Visual field testing (Octopus or Humphrey)	X					X	X	X	X	x	X
Optic disc photograph of the optic nerve	x					x	x	x	x	x	x
Vertical C/D ratio	X					X	X	X	X	x	X
Central corneal thickness (pachymetry)	X							X	X	x	X
Gonioscopy, angle grading using Shaffer grading	X										

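### Does aiming for 16 completers at month 6 contradict enrolling 25 patients with 25% dropout?

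*Combined protocol and SAP*

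**What the plan says.** The Sample Size row of the Synopsis uses a two-sided paired t-test "with alpha of 0.05 and power of 0.9". "The difference of interest is taken equal to 5.2 mmHg". Dropout then enters by diluting the effect. "Under the conservative assumption that 25% of subjects will drop out of the study", the effect becomes 0.75 × 5.2 = 3.9 mmHg "if all patients are included in an ITT analysis". The variance of the change is capped at 3² + 5² = 34, giving an SD of 5.83. "Under these assumptions, the sample size required is equal to 25 patients".

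The next row, Statistical rationale for sample size calculation, gives the source of the 5.2 mmHg. Mean baseline IOP is 26.0 mmHg (SD 3.0). The sentence beginning "The mean IOP at 6 months is estimated to" gives 20.8 mmHg (SD 5). The row ends: "Based on these assumptions, the estimated sample size of 25, in order to obtain 16 completed subjects at 6 Months follow-up". It does not mention dropout or say how 16 was derived.

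The Design row agrees on enrolment: "In total 25 patients will be enrolled in approximately 5 sites".

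**The concern.** The two rows appear to describe one calculation but give different completer counts. At 25% dropout, 25 enrolled patients leave 18 to 19 completers. Sixteen of 25 would mean losing 36%, a rate that appears nowhere. Working backwards, 16 / 0.75 = 21.3, so 22 enrolled would be expected to yield 16. Neither direction links 25 and 16 at the stated rate.

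Month 6 is the time point of the primary objective, and this sentence is the only one in the synopsis that says how many patients should have data there. If 16 were a forecast, the 25% used to dilute the effect would be too low and the 90% power claim would be overstated. The rationale also ties the 25 to a completer target, whereas the Sample Size row obtains it from an analysis of all patients.

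**Working it through.** **Inputs.** From the Sample Size row: paired t-test, two-sided alpha 0.05, power 0.90, SD 5.83, effect 5.2 mmHg undiluted and 3.9 mmHg diluted, dropout 25%, N = 25. From the rationale row: 26.0 − 20.8 = 5.2 mmHg, and a target of 16 completers.

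**Step 1: reproduce the 25.** The normal approximation is n = ((z₀.₉₇₅ + z₀.₉₀) × SD / δ)². With SD 5.83 and δ = 3.9 this is 23.5. Adding the usual t correction, z₀.₉₇₅² / 2 = 1.92, gives 25.4. Exact noncentral-t power is 89.4% at n = 25 and 90.6% at n = 26. The stated 25 is therefore reproduced to within one patient and 0.6 percentage points of power. The variance of 34 is stated as an upper limit. It is also the value for uncorrelated baseline and month-6 readings; positive correlation would lower it and raise the power.

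**Step 2: expected completers.** 25 × (1 − 0.25) = 18.75, so 18 to 19.

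**Step 3: what 16 could be.** Keep the same test, alpha, power and SD, but use the undiluted 5.2 mmHg, the effect expected in patients who stay in the study:

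| Completers | Power at 5.2 mmHg |
|---|---|
| 15 | 89.4% |
| 16 | 91.5% |
| 18 | 94.6% |
| 19 | 95.7% |

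Sixteen is the smallest number reaching 90%. Other settings also give 16 (3.9 mmHg, one-sided, with SD 5.83 and 80% power or SD 5 and 90% power), but they depart from the plan's stated test or inputs.

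**Step 4: does enrolling 25 secure 16?** Treat each patient as completing month 6 independently with probability 0.75 and take the binomial chance of at least 16 completers:

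| Enrolled | P(at least 16 complete) |
|---|---|
| 22 | 69.9% |
| 23 | 80.4% |
| 24 | 87.9% |
| 25 | 92.9% |

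Twenty-five is the smallest enrolment with at least a 90% chance of 16 completers. The 22 obtained from 16 / 0.75 would fall short of 16 about 30% of the time. The synopsis does not claim to have used this calculation, but it shows that 25, 16 and 25% can all hold together.

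**The case for a change.** The strongest case for a change is that the sentence presents 25 as following from the assumptions above it and as serving to reach 16, yet no stated step leads from one to the other. A minimum should be labelled as such and its derivation given. If the sponsor really expects only 16 completers, the plan's own dilution would give 0.64 × 5.2 = 3.33 mmHg and about 78% power at N = 25, well below 90%. The two rows also give different reasons for the 25. A one-sentence clarification would cost almost nothing.

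Part of this stands. The synopsis does not say whether 16 is a minimum or a forecast, and the two rows are loosely joined. The damaging reading, however, needs a 36% loss that the text never states and that conflicts with its description of 25% as conservative. The wording about obtaining 16 describes a goal, and a goal below the expected count is no contradiction. If the 25% covers all 24 months, completers at month 6 would be 18 to 19 or more, further above 16. The document supplied is also only a synopsis, so it cannot be said that the 16 is unexplained in the full investigational plan.

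**Conclusion.** The concern compares a required minimum with an expected count, and the difference of 2 to 3 patients is not an arithmetic error. Enrolment of 25 stands on the intention-to-treat calculation, with 89.4% exact power at the largest variance the plan allows, a rounding-level difference from 90%. If 16 patients complete, an analysis of completers at 5.2 mmHg still has 91.5% power; with the expected 18 to 19 it has about 95% to 96%.

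This rests on reading 16 as a minimum, which is inferred from the wording and from the match with the undiluted calculation, and on 25% dropout by month 6, independent between patients for the 92.9% figure. On that reading, labelling the 16 would alter neither the number enrolled, nor the analysis, nor the power claim. It is a missing explanation with no consequence for the trial, and no change follows.

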To test the reduction in medicated diurnal IOP between screening/baseline visit and medicated diurnal IOP 12 months and 24 months after surgery.

To assess the safety of the MINIject in terms of nature and severity of Adverse Events (AE/SAE), Adverse Device Effects (ADE/SADE) and Unanticipated Adverse Device Effect (UADE)*.

To assess the rate of peripheral and central corneal endothelial cells density-loss.

To assess the rate defined as:

- Complete success: diurnal IOP \leq 21mmHg and $>$ 5mmHg with a minimum 20% diurnal IOP reduction from baseline without the need for glaucoma hypotensive medication.
- Qualified success: diurnal IOP \leq 21mmHg and $>$ 5mmHg with a minimum 20% diurnal IOP reduction from baseline with the concomitant use of glaucoma hypotensive medication.

To assess the reduction of the number of hypotensive active ingredients compared to screening visit.

Synopsis

* referring to expected AEs for implantable glaucoma devices as listed in ANSI Z80.27.2014 and FDA Guidance Premarket Studies of Implantable Minimally Invasive Glaucoma surgical (MIGS) Devices.

Assessed Parameter	The assessed parameters are listed in detail in Table 1 at the end of this synopsis.

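### Do the 25 patients sized on an all-patient analysis and the target of 16 completers leave the primary 6-month IOP test undefined?

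*Combined protocol and SAP*

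**What the plan says.** The Primary study objective row sets the endpoint: "The primary objective is to show a reduction in medicated diurnal IOP between screening/baseline visit and medicated diurnal IOP at 6 months after surgery".

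The Sample Size row uses a two-sided paired t-test with alpha 0.05 and power 0.9. The difference of interest is 5.2 mmHg and the SD of the change is 5.83. It then allows for loss: "Under the conservative assumption that 25% of subjects will drop out of the study", the effect becomes 0.75 × 5.2 = 3.9 mmHg "if all patients are included in an ITT analysis". The result is 25.

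The row on the statistical rationale for the sample size gives the means behind the 5.2 (26.0 mmHg at baseline, 20.8 mmHg at 6 months) and closes with "the estimated sample size of 25, in order to obtain 16 completed subjects at 6 Months follow-up (endpoint for the primary objective". It also says that an IOP reduction of at least 20% "has been previously used as success criterion and thus can be defined as clinically meaningful".

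In the Design row and the flow chart (Table 1), diurnal IOP is taken at screening/baseline and at months 6, 12, 18 and 24. From day 1 to month 3 there is only a "single point IOP measurement".

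The synopsis does not name a primary analysis set or say how a missing month-6 diurnal value is treated.

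**The concern.** The two sample size rows seem to describe different tests. The first counts all 25 patients and lets drop-outs pull the effect down. The second counts patients who reach month 6, and 16 is also the number that a completer test at the undiluted 5.2 mmHg would need. The stated drop-out does not connect them: 25 × 0.75 = 18.75, and 16 of 25 is a 36% loss.

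The all-patient test also lacks an input. A patient who leaves before month 6 has no diurnal IOP after surgery, so a paired t-test has nothing to use for that patient unless a rule supplies a value. Without a rule the test falls back on completers, which is not the analysis that gave 25.

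At stake is the size of the reported reduction. In an open study with one cohort, that is the main result. On the plan's assumptions the all-patient mean is 3.9 mmHg (15% of 26.0) and the completer mean is 5.2 mmHg (20%). If nothing fixes the set, it could be picked once the data are known. A similar question arises for the secondary tests at 12 and 24 months.

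**Working it through.** **Inputs.** From the Sample Size row: paired t-test, two-sided alpha 0.05, target power 0.9, effect 5.2 mmHg (3.9 after dilution), 25% drop-out, SD = √(3² + 5²) = √34 = 5.83. From the rationale row: baseline mean 26.0 mmHg and 16 completers. Power is from the non-central t distribution with n − 1 degrees of freedom and non-centrality d√n / 5.83.

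**1. The plan's own figure.** At d = 3.9, n = 25 gives power 0.894 and n = 26 gives 0.906. The stated 25 reproduces to within one patient.

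**2. The figure of 16.** At d = 5.2, n = 15 gives 0.894 and n = 16 gives 0.915. Sixteen is therefore the smallest number of completers with 90% power at the undiluted effect. The synopsis does not say that it was obtained this way; the match is an inference.

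**3. Do the two conflict?** Expected completers at 25% loss are 25 × 0.75 = 18.75, which is above 16. Completer power is 0.946 with 18 and 0.957 with 19. Read as a minimum, 16 fits beside 25 enrolled and leaves a margin of two to three patients.

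**4. Does the set matter for the primary test?** Let m patients complete and give the other 25 − m a change of zero, which is what the 0.75 factor implies for the mean. Write p = m/25, c = t(0.975, 24) = 2.064, and T for the completers' t statistic. The t-test on all 25 is significant when

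T² > c²(m − 1) / [24p − c²(1 − p)].

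- m = 19: 4.260 × 18 / (18.24 − 1.022) = 76.67 / 17.22 = 4.453, so T > 2.110. The completer test needs T > 2.101.
- m = 16: 4.260 × 15 / (15.36 − 1.533) = 63.90 / 13.83 = 4.621, so T > 2.150. The completer test needs T > 2.131.

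| Completers | Power, all 25 (drop-outs at no change) | Power, completers only |
|---|---|---|
| 19 | 0.956 | 0.957 |
| 16 | 0.912 | 0.915 |

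The zeros lower the mean and the spread together, so the two tests nearly coincide.

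**5. Does the set matter for the estimate?** With drop-outs at no change, the expected all-patient mean is 5.2 × m/25.

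| Loss | All-patient mean | Completer mean |
|---|---|---|
| 25% | 3.90 mmHg (15.0% of 26.0) | 5.20 mmHg (20.0%) |
| 36% (16 complete) | 3.33 mmHg (12.8%) | 5.20 mmHg (20.0%) |
| 10% (assumed, if 25% is a 24-month rate) | 4.68 mmHg (18.0%) | 5.20 mmHg (20.0%) |

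The gap is real but depends on the no-change assumption. If drop-outs instead kept 80% of the completer effect (an illustrative assumption), 19 completers would give (19 × 5.2 + 6 × 4.16)/25 = 4.95 mmHg against 5.20.

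**The case for a change.** The best argument for a change is that the remedy is cheap and the gap is genuine. A few sentences would name the set and the missing-value rule, at no cost in enrolment, visits or alpha. The estimate moves by 1.3 mmHg at 25% loss. It moves across the 20% mark that the synopsis itself calls clinically meaningful: if the true completer reduction is exactly 5.2 mmHg, the two means fall on opposite sides of 5.2 mmHg in about 39% of trials with 19 completers.

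Part of this stands. The synopsis is silent on both points, and 16 sits oddly beside a 25% drop-out. The rest carries less weight:

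- The 39% measures disagreement about a decision that the plan does not make. The primary objective is to show a reduction. In the Secondary study objectives, 20% is a per-patient success criterion, and in the rationale row it supports the choice of effect. Nothing makes a mean reduction of 20% a pass mark.
- The rationale row gives a number of patients to obtain and does not name a second analysis set. The only analysis named is the all-patient one, and the 0.75 factor already shows how drop-outs were meant to count in the mean.
- The available text is the synopsis of the Clinical Investigational Plan. Analysis sets and missing-data rules normally sit in the fuller plan, so the silence here does not show that the set is open to choice afterwards.
- No clearly better rule is on offer. Counting drop-outs as unchanged is itself debatable. Extending it to months 12 and 24 would ignore diurnal values already measured at months 6, 12 or 18 in patients who leave later.

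**Conclusion.** No change to the plan is needed. The sample size of 25 and the target of 16 each follow from the stated inputs and can hold together, with 16 as a minimum and 18 to 19 expected. The primary test against zero has practically the same power on either set: the difference is 0.001 with 19 completers and 0.003 with 16. The estimates do differ, by 1.3 mmHg at 25% loss if drop-outs are counted as unchanged, but no stated success rule depends on that difference.

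The missing set and missing-value rule are details that a competent analyst would settle before analysis: report the all-patient result on which the study was sized and show the completers beside it. A low-priority question to the sponsor is reasonable, asking what 16 represents and whether the full plan states the set and the rule, with months 12 and 24 treated separately.

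This rests on three assumptions: the planning SD of 5.83 holds, patients who leave do not differ systematically from those who stay in what their reduction would have been, and only the synopsis could be examined.

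### Does the 12:00 AM label on the middle diurnal IOP reading in the flow chart put the primary endpoint at risk?

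*Combined protocol and SAP*

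**What the plan says.** The ocular part of the flow chart (Table 1 of the synopsis) has one row for the diurnal pressure: "IOP, Goldmann Appl. Tonometry, diurnal (8:00 AM, 12:00 AM, 4:00 PM". It is marked at Visit 0 and at months 6, 12, 18 and 24. From 1 day to 3 months a separate row asks for a single reading with no clock time. The note under Table 1 deals only with which eye is examined.

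The endpoints rest on this row. The Primary study objective section of the synopsis states: "The primary objective is to show a reduction in medicated diurnal IOP between screening/baseline visit and medicated diurnal IOP at 6 months after surgery". Under Secondary study objectives, the reductions at months 12 and 24 are tested, and complete success needs a pressure of at most 21 and above 5 mmHg, "with a minimum 20% diurnal IOP reduction from baseline without the need for glaucoma hypotensive medication". None of these sections restates the clock times or says how the three readings are combined.

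The Design section adds: "In total 25 patients will be enrolled in approximately 5 sites in Panama, India and Europe (France or Germany". There is one cohort and no control arm.

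**The concern.** By the usual convention 12:00 AM is midnight. A site that followed the cell to the letter would take two daytime readings and one at night, and would call the result diurnal. The cell is an instruction to sites in several countries, and it is the only statement of the times in the posted text.

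What would be at stake is the within-patient change in pressure. If a patient's middle reading were taken at midday at baseline and at midnight at month 6, or the reverse, the paired difference would include a time-of-day component that has nothing to do with the implant. With no control arm, nothing would cancel it.

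**Working it through.** **Step 1: which reading fits the row.** In 24-hour notation the two candidates are:

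- midday: 08:00, 12:00, 16:00. The times ascend, the gaps are 4 h and 4 h, and all three are in the daytime;
- midnight: 08:00, 00:00, 16:00. Midnight comes before the first time or after the last, never between them, and it contradicts the row's own label.

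Only midday is consistent with the order, the spacing and the word diurnal.

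**Step 2: when the label could bias the primary comparison.** Write each reading as the patient's level at that visit plus a clock component c(t). Assume that diurnal IOP is the mean of the three readings (the document does not say). With middle reading times m0 at baseline and m6 at month 6, the clock component left in the paired difference is

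(c(m6) − c(m0)) / 3.

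This is zero whenever m0 = m6, whatever the hour. Sites may even differ from one another without adding a shift, as long as each patient is measured at the same times at both visits. One row fixes the times for all five diurnal visits, so the plan already prescribes m0 = m6.

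**Step 3: size if it went wrong anyway.** Assume that midnight and midday differ by s = 2 to 6 mmHg. No figure in the document supports this; it is a range for illustration. A discordant patient's own change moves by s/3, which is 2/3 = 0.67 to 6/3 = 2.0 mmHg. It would be wrong to divide that by 5.2 mmHg, because 5.2 is the planned group mean. With k discordant patients of N, all shifted in the same direction, the group mean moves by k × s / (3N):

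| k of N | Shift in group mean (mmHg) | Share of 5.2 mmHg |
|---|---|---|
| 1 of 25 | 0.67/25 = 0.03 to 2.0/25 = 0.08 | 0.5% to 1.5% |
| 5 of 25 | 5 × 0.67/25 = 0.13 to 5 × 2.0/25 = 0.40 | 2.6% to 7.7% |
| 1 of 16 | 0.67/16 = 0.04 to 2.0/16 = 0.13 | 0.8% to 2.4% |
| 5 of 16 | 5 × 0.67/16 = 0.21 to 5 × 2.0/16 = 0.63 | 4.0% to 12.0% |

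The rows with N = 16 use the number of completers at month 6 that the sample size rationale aims for. A shift of 0.67 to 2.0 mmHg in the group mean (13% to 38% of 5.2) would need every patient to be discordant in the same direction.

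**Step 4: sample size.** The plan says "Sample size is obtained by a paired sample t-test, 2-sided, with alpha of 0.05 and power of 0.9", and "The difference of interest is taken equal to 5.2 mmHg". It dilutes that difference for 25% dropout to 0.75 × 5.2 = 3.9 mmHg, with the standard deviation √(3² + 5²) = √34 = 5.83.

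- Normal approximation: n = ((1.960 + 1.282) × 5.83 / 3.9)² = 23.5, so 24.
- Exact paired t-test: n = 26; power at n = 25 is 89.4%.
- Exact paired t-test with the undiluted 5.2 mmHg: n = 16, power 91.5%. This agrees with the 16 completers.

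The stated 25 is reproduced to within one patient. No clock time enters any of these formulas, so the label changes neither the number nor the power.

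**The case for a change.** The strongest case for acting has four parts.

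- **The cell is wrong as printed and nothing corrects it.** This stands. It is limited by the fact that the posted text is a synopsis; whether sites had fuller measurement instructions cannot be told from it.
- **The trial is exposed.** There is one arm, about five sites and 16 planned completers, so a few inconsistent patients would carry weight. Step 3 shows the weight: five of 16, all shifted the same way and at the top of the assumed range, would move the mean by 12% of the planned effect. That needs sites to change their reading of one cell between two visits of the same patient, and the document gives no reason to expect it.
- **Consistency does not rescue absolute limits.** This is correct. If a site used midnight throughout, the difference would be free of a time-of-day shift, but the 21 mmHg success limit would be judged on another mix of hours. So would the 21 to 35 mmHg eligibility range, which Visit 0 appears to draw from the same row. The percentage criterion would also move a little: planned figures give 5.2/26.0 = 20.0%, while a baseline higher by 0.67 or 2.0 mmHg gives 5.2/26.67 = 19.5% or 5.2/28.0 = 18.6%. All this depends on a site adopting the one reading that the row itself rules out.
- **Correcting the cell is cheap.** That is so, but it is a proofreading correction. It would write down what the row already conveys, and a demand for the same times at every diurnal visit would repeat what the single row already sets.

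**Conclusion.** The label is a clerical slip and no change to the plan follows. The row's order, spacing and heading all point to midday, and one row sets the same times for baseline and every diurnal follow-up visit, so the paired comparison at month 6 is sound as planned. Sample size and power are untouched.

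No effect on the primary endpoint can be calculated from the document alone. Under the assumed 2 to 6 mmHg gap and a mean of three readings, one patient measured inconsistently shifts the group mean by 0.03 to 0.08 mmHg of a planned 5.2 mmHg.

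The conclusion rests on sites reading the row as a daytime series, or at least reading it the same way at each visit of a given patient. Evidence that a site switched between visits would reopen the point; the document contains none.
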